## **LIST OF ABBREVIATIONS**

AE: Adverse event

AF: Atrial flutter

AET: Atrial ectopic tachycardia

AV: Atrioventricular

AVRT: AV reentrant tachycardia

BID: Twice a day

BP: Blood pressure

Bpm: Beats per minute

CRFs: Case report forms

DSMB: Data & Safety Monitoring Board

ECG: Electrocardiogram

ECHO: Echocardiography

F/M: Fetal/maternal

HR: Heart rate

IUD: Intrauterine demise

NND: Neonatal death

PJRT: Permanent junctional reciprocating tachycardia RCT: Randomized Clinical Trial

REB: Research Ethics Board

SAE: Serious adverse event

SAR: Serious adverse reaction

SUADR: Serious Unexpected Adverse Drug Reaction

SVA: Supraventricular tachyarrhythmia

SVT: Supraventricular tachycardia

TID: Three times a day

WPW syndrome: Wolff-Parkinson-White syndrome

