## 1. INTRODUCTION

Although fetal supraventricular tachyarrhythmias (SVAs), including atrial flutter (AF) and other forms of supraventricular tachycardia (SVT), are the most common causes of intended in-utero fetal therapy, none of the drugs used has ever been evaluated for their effects on the mother and her child in a Randomized Clinical Trial (RCT). In the absence of such evidence, there is no consensus for the optimal management. The *Fetal Atrial Flutter and Supraventricular Tachycardia (FAST) Therapy Trial* is a prospective multi-centered trial that addresses this knowledge gap to guide future fetal SVA therapy to the best of care.

Study components of the FAST Therapy Trial include:

- **Three prospective RCT sub-studies (FAST RCT)** to determine the efficacy and safety of specific transplacental drug regimens in suppressing fetal AF without hydrops, SVT without hydrops, and SVT with hydrops. Additional information on the RCT sub-studies is available at ClinicalTrials.gov under listing #NCT02624765. Participation in the regulated FAST RCTs is currently restricted to pre-selected centers.

**A prospective observational cohort study (FAST Registry)** is a non-regulated Registry which seeks to establish an international database of fetal SVA management done to date, to be used to publish information on the results of current prenatal care and to evaluate the need for additional FAST RCTs. Participation in FAST Registry requires site REB approval and an executed legal contract with the Hospital for Sick Children, Toronto (REB Number# 1000048953).

- 

This protocol applies to centers that are participating in the RCT sub-studies.

The **primary outcome** of the FAST RCT will be the proportion of term deliveries of live-born children with a normal cardiac rhythm. Term delivery is defined as birth 37 0/7 weeks gestation or later. **Secondary outcomes** will determine the efficacy of 1st line, 2nd line, 3rd line, and maintenance drug therapy in controlling the different arrhythmias prior to birth and patient safety. We expect faster cardioversion to be significantly associated with higher rates of normal term deliveries and less perinatal mortality, morbidity and resource utilization due to shorter hospitalization.

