- **FLECAINIDE** inhibits Na+ channels, slowing conduction and increasing refractoriness of all cardiac tissues. Flecainide is well-absorbed and transferred to the fetus to reach therapeutic levels within 3 days (F/M ratio 0.7-0.9). At maternal serum concentrations >1 mcg/ml, the QRS interval may prolong and the risk of proarrhythmia increase. Infrequent maternal AEs include blurred vision, nausea, constipation, dizziness, and headache. Maternal SAEs have not been reported but there is one case of unexplained in-utero demise of a non-hydropic fetus 23 years ago.
- **SOTALOL** is both an iKr channel and β-blocker, with β-blockade as the main effect at doses <160 mg/day. The combined effects decrease heart rate, and prolong action potential duration and tissue refractoriness throughout the heart. Sotalol is well absorbed and transferred to reach a fetal steady state level similar to maternal plasma level (F/M ratio 0.7-2.1). The agent is usually well-tolerated and maternal SAEs have not been reported. Maternal sotalol up to 480 mg/day did not cause significant prolongation of neonatal QTc. Symptoms related to β-blockade may include fetal or maternal bradycardia. There is a single case of unexplained fetal death in the absence of fetal hydrops in the literature.

In *summary*, antiarrhythmics act on one or several ion channels and/or the autonomous system. Drug-specific differences in actions and pharmacokinetics likely predetermine the potential of a compound in terminating and, once achieved, in suppressing SVA recurrence. AVRT involves myocardium, the AV node and accessory pathway(s) in the reentrant circuit. Alteration of the conduction and refractoriness properties of any of these tissues may terminate AVRT. **Digoxin** prolongs AV nodal refractoriness. If the prolongation is sufficient, reentry will terminate because the AV node becomes refractory to premature depolarization. **Flecainide** delays the

[figure not shown]

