**2.6 SAFETY OF TRANSPLACENTAL THERAPY** There is extensive retrospective data on the safe use of digoxin, sotalol, and flecainide, either alone or when used in combinations for this indication, with the limitation that AEs were most likely inconsistently documented and thus underreported in retrospective studies. Although minor drug-related AEs are not infrequent patient complaints based on our own retrospective experience and drug monographs, life-threatening AEs owing to the use of fetal antiarrhythmic drug therapy in predominantly healthy mothers have not been reported. However, virtually all antiarrhythmic agents may have the potential to provoke new or to exacerbate existing arrhythmias. This risk increases with toxic drug levels, maternal heart disease, ventricular arrhythmia, and hypokalemia. Previously reported mortality rates of treated fetuses with SVA *without* hydrops were between 0% and 5%, whereas about 20% of fetuses with SVA *with* hydrops had died, usually due to treatment-resistant SVA. In our large experience, we never observed unexpected SAEs, irrespective whether single or multiple drug therapy was used.

*To minimize risks of SAEs* a) only mothers without serious health and pregnancy concerns other than fetal SVA are eligible for participation in the RCTs (**see Section 7.2**); b) the primary physician and participant both are informed about the assigned drug therapy from the time of randomization to study end (open label trial); c) drug dosages will be used that are considered to be safe and effective (**see 7.6**), thus avoiding toxic levels (digoxin) and excessive QTc prolongation >0.5 (sotalol); and d) initiation of therapy is recommended in-hospital to monitor maternal/fetal heart rates and wellbeing, followed by serial outpatient encounter once arrhythmia control is achieved (**see 7.7**).

[figure not shown]

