#### **PRIMARY OUTCOME**

- Term delivery ( $\geq 37$  0/7 weeks gestation) with a normal cardiac rhythm (ECG).

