#### **SECONDARY OUTCOME**

- Proportion of participants with cardioversion over time
- Proportion of participants with treatment failure
  - Number of participants with treatment failure compared to number of participants with successful treatment.
  - Treatment failure is defined as one of the following:
    1. cross-over to another drug
    2. SVT/AF that persists to birth
    3. preterm birth
    4. death
- Cause of death (prenatal, postnatal)
- Proportion of participants with arrhythmia related death
- Average gestational age at birth
- Birth weight (z-scores)
- Average days of maternal and neonatal hospitalization related to SVA therapy
- Maternal prevalence of pregnancy/treatment-related AEs and outcomes
- Proportion of AEs / adverse outcomes (prenatal, postnatal)

The primary outcome measure is absolute (term delivery without tachyarrhythmia) with no room for interpretation. Secondary outcomes will be the time interval from treatment initiation to the beginning of permanent cardioversion, and once established, the freedom from SVA recurrence on maintenance therapy. Only the final outcome will be considered to classify cases. Cross-over to another agent, fetal demise, development of fetal hydrops, and delivery for SVA will be considered treatment failures. Any recurrence of fetal SVA after

documentation of a normal cardiac rhythm >24 hours by echocardiography will be classified as maintenance treatment failure.

**7.11 STATISTICAL ANALYSES.** All statistical analyses using SAS (SAS Institute, Cary NC) with standard settings will be performed by very experienced statistician from the Cardiovascular Data Management Centre (CVDMC) at SickKids. As a general precept, all 3 RCTs will be analyzed separately. RCT analyses will be performed on an *intention-to-treat basis*, although a separate subgroup analysis will be performed. Descriptive statistics for all study variables, for each study groups separately, will be created using means with standard deviation, median with inter-quartile range, and frequencies as appropriate. Baseline characteristics that should be equally distributed between groups through randomization (age at diagnosis, baseline fetal heart rate, incessant vs. intermittent SVA, maternal age) will be assessed in a test of randomization. The test of randomization will be performed using Fisher’s exact test for categorical variables and Student’s t-test (with Satterthwaite method for variance estimation) for continuous variables.

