The **PRIMARY OUTCOME** (proportion of term deliveries without SVA) will be a binary outcome (yes/no). For this type of outcome, the proportion of participants in each therapy arm will be compared using logistic regression models (PROC LOGISTIC) with likelihood ratio test to determine regression model fit, Wald chi-square test from maximum likelihood estimates (Fisher’s scoring technique) to determine statistical significance of the therapy arm and c-statistic from the regression model’s area under the curve (AUC) to measure model accuracy. Effect size estimate and standard error will be converted into odds ratio with 95% confidence (95% CI) limits to facilitate comparisons between the different trials.

**SECONDARY OUTCOME** will also be expressed as binary variables (incl. proportions of participants: requiring 2nd line therapy and 3rd line therapy; with SVA recurrence on maintenance therapy; delivery without SVA termination; death <1 month; etc.) will be assessed between the different therapy arms in the same way as the primary outcome. For outcomes with time dependent variables (proportion of participants with cardioversion over time; timing of mortality from initiation of therapy), Kaplan-Meier survival curves will be used to depict the event proportion over time for each group. Single phase parametric hazard regression model (PROC PHREG) will be used to compare the 2 therapy arms (with likelihood ratio test to determine regression model fit and maximum likelihood estimates chi-square to determine statistical significance of the therapy arm. Effect size estimate and standard error will be converted into hazard ratio with 95% CI to facilitate comparisons between the different trials. Finally, for outcomes with continuous variables (average gestational age at birth/birth weight z-score; average days of neonatal hospitalization related to SVA therapy), linear regression models using maximum likelihood estimates for parameter estimation will be used (PROC GENMOD: Akaike's information criterion (AIC) criterion to assess regression model fit; Wald chi-square test from maximum likelihood estimates). Effect size estimate and standard error will determine the difference between the therapy arms in the same original units of measurement as the outcome.

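### The primary outcome has four non-equivalent wordings, and the one in 7.11 that feeds the primary test counts a term newborn with a rhythm disorder other than SVA as a success

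*Combined protocol and SAP*

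**What the plan says.** The same endpoint is described in four places in the combined protocol and SAP.

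- Section 1, Introduction: "the proportion of term deliveries of live-born children with a normal cardiac rhythm". Being alive at birth is part of the rule; no ECG is mentioned.
- Section 7.10, the entry under Primary Outcome: term delivery "with a normal cardiac rhythm (ECG"). An ECG is named; live birth is not.
- Section 7.10, the narrative after the list of secondary outcomes: "The primary outcome measure is absolute (term delivery without tachyarrhythmia) with no room for interpretation". Neither live birth, ECG nor normal rhythm appears.
- Section 7.11, Primary Outcome: "proportion of term deliveries without SVA) will be a binary outcome (yes/no". This is the variable entered in the logistic regression.

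The List of Abbreviations gives "SVA: Supraventricular tachyarrhythmia", so bradycardia, AV block and ventricular arrhythmia are not SVA. Death is scored as a failure under treatment failure in 7.10, which is a secondary outcome.

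**The concern.** A binary primary endpoint needs one rule that classifies every participant the same way whoever applies it. Here the text that defines the analysis variable is looser than the text that defines the endpoint, and the plan nonetheless asserts that no interpretation is needed.

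The gap lies where the study drugs could act. Section 2.4 says of sotalol: "Symptoms related to β-blockade may include fetal or maternal bradycardia". It also describes digoxin as slowing the sinus node and prolonging AV nodal refractoriness, and flecainide as slowing conduction. Section 2.6 says that "virtually all antiarrhythmic agents may have the potential to provoke new or to exacerbate existing arrhythmias". A rule that looks only for SVA would score such an effect, if present at a term birth, as a success.

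The endpoint is used more than once. It is the primary test in each of the three RCTs, the focus of the interim analysis at 50% of enrolment (7.11) at which an RCT may stop for benefit at p < 0.001 (5.4), and the dependent variable of the sub-analysis (7.11). The trial is open label, which is a further reason to settle the rule before outcomes are compared by arm.

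**Working it through.** **Step 1. Apply each wording to the same cases.** All cases are deliveries at or after 37 0/7 weeks.

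| Case | Section 1 | 7.10 list | 7.10 narrative | 7.11 |
|---|---|---|---|---|
| Alive, normal rhythm on ECG | success | success | success | success |
| Alive, SVA | failure | failure | failure | failure |
| Alive, bradycardia or AV block | failure | failure | success | success |
| Alive, ventricular tachyarrhythmia | failure | failure | failure | success |
| Stillborn | failure | cannot be met (no normal ECG) | not excluded | not excluded |

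The disagreement already exists inside 7.10, whose narrative is close to 7.11. The narrative and 7.11 are not identical either, because tachyarrhythmia is wider than SVA.

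**Step 2. Reproduce the plan's sample size, to see whether it is touched.** Inputs from 3.2: 30% vs 50% (RCT A and C), 55% vs 75% (RCT B), two-sided 0.05, power 80%, equal arms. With the pooled-variance formula

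n per arm = [1.960·√(2p̄(1−p̄)) + 0.842·√(p₁(1−p₁)+p₂(1−p₂))]² / (p₂−p₁)²

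- A, C: p̄ = 0.40; [1.960·√0.48 + 0.842·√0.46]² / 0.04 = 93.
- B: p̄ = 0.65; [1.960·√0.455 + 0.842·√0.435]² / 0.04 = 88.1, rounded up to 89.
- Total 186 + 178 + 186 = 550.

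These are the stated figures. Choosing one wording alters no input, so they stand.

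**Step 3. Size per reclassified infant.** 1/93 = 1.08 points (A, C) and 1/89 = 1.12 points (B). Against the planned 20 points that is 5.4% and 5.6% of the effect per infant.

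**Step 4. Size under an assumed rate.** The documents give no rate of non-SVA rhythm disorder at birth. Assume 2–5% of term, SVA-free births in one arm are affected. The primary proportion is taken over all participants, so this rate must be multiplied by the share who are term and SVA-free. The planned success proportions serve as an approximation to that share.

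- A, C: 0.02 × 30% = 0.6 points, up to 0.05 × 50% = 2.5 points. With 93 per arm: 0.6 to 2.3 infants.
- B: 0.02 × 55% = 1.1 points, up to 0.05 × 75% = 3.75 points. With 89 per arm: 1.0 to 3.3 infants.

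**Step 5. What a shift of that order does to the test.** Take the section 1 rule as the truth, at the planned rates, and let 7.11 inflate one arm only.

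| Inflation of one arm | Power if it is the inferior arm: A, C | B | False-positive rate if the arms are truly equal (30% or 55%): A, C | B |
|---|---|---|---|---|
| 0 | 80.0% | 80.4% | 5% nominal | 5% nominal |
| 1 point | 75.6% | 76.4% | 5.3% | 5.2% |
| 2 points | 70.7% | 72.1% | 6.0% | 5.8% |

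For an arm at the inferior rate, Step 4 gives 0.6–1.5 points in A or C (up to 0.05 × 30%) and 1.1–2.75 points in B (up to 0.05 × 55%). The 2-point row is therefore already beyond the assumed range for A and C. If both arms are inflated equally by 1 or 2 points, power stays between 79.4% and 81.5%.

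**The case against.** The best defence is that 7.11 is a paragraph about the model and its parenthesis merely labels an endpoint defined elsewhere. A statistician who turned back to section 1 or the 7.10 list would score the disputed cases as failures. This carries most weight for stillbirth: section 1 says live-born, a stillborn child cannot show a normal ECG, the forms separate birth from demise, fetal demise is a treatment failure in 7.7 and 7.10, and the earlier retrospective study described in 2.5 counted perinatal death as adverse. Scoring a term stillbirth as success is therefore a strained reading, though the words of 7.11 do not rule it out. The defence does not settle the rhythm question. That earlier composite asked only about persistent SVA, so an SVA-only rhythm rule is a live reading rather than an obvious slip, and the 7.10 narrative supports it.

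It is also fair to say that rhythm harm is not ignored: adverse events and adverse outcomes are secondary outcomes, and the interim analysis reviews them between groups.

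A reader might infer more than the documents support:

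- *That the looser rule favours the sotalol arm.* Section 2.4 speaks of fetal or maternal bradycardia, not of a neonatal disorder at term, and reports no significant neonatal QTc prolongation with sotalol up to 480 mg/day. Digoxin, the comparator in RCT A and present in both arms of RCT C, acts on the sinus and AV nodes, and flecainide slows conduction. No direction follows, and RCT B has no sotalol arm.
- *That the forms cannot record another abnormal rhythm.* The Table of Events in section 7 lists neonatal ECGs in sinus rhythm and in SVA, but 7.8 asks for upload of a neonatal ECG without that limit, and the case report form is not among the documents.

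**Conclusion.** The point stands as a conflict between stated definitions of the primary endpoint, and it should be corrected before outcomes are compared by arm. That the four wordings differ, and that no text ranks them, is certain. The case that matters most is the live term newborn with a non-SVA rhythm disorder; the term stillbirth is secondary.

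The size is uncertain and probably modest: about 1.1 points per infant, and 0.6–2.5 points (A, C) or 1.1–3.75 points (B) under the assumed 2–5%, which is some one to three infants in an arm. This rests on an assumed rate, on all affected births falling in one arm, and on planned success proportions standing in for the share of term, SVA-free births. It would be wrong to read 2–5% of term newborns as a 2–5 point shift, because the denominator is all participants. A shift of 5 points in one arm, which would take power to 54.4% in A or C, lies outside the range derived here. Because the drugs differ in their rhythm effects, the cases may differ between arms, but the documents do not say which arm would gain.

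**What to change.** Use one definition, word for word, in sections 1, 7.10 and 7.11: live birth at or after 37 0/7 weeks with a normal cardiac rhythm on neonatal ECG. State that stillbirth and any abnormal rhythm, whether SVA, bradyarrhythmia, AV block or ventricular arrhythmia, are scored as failure. Remove absence of SVA and absence of tachyarrhythmia as definitions of the endpoint. Check that the neonatal ECG record can capture an abnormal rhythm other than SVA, and add an option only if it cannot.

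The cost is wording in three sections and possibly one data field. The observed success proportion may be slightly lower than under the 7.11 wording. The targets of 93, 89 and 93 per arm and the total of 550 are unchanged.

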**Fig. 2. Freedom from termination of fetal SVT with and without hydrops (n=75).** Treatment failure was also more likely if SVT was associated with fetal hydrops (HR=1.8; p=0.04) at the time of diagnosis. It took more than twice as long (9 vs. 4 days) for conversion of 50% of SVT cases to a normal rhythm if fetuses were hydropic. 21% of the hydropic cases died.

[figure not shown]
lower cardioversion rates. On the other hand, 1st line monotherapy with sotalol resulted in faster/higher AF termination rates [Fig. 3] while flecainide or digoxin was superior in terminating SVT [Fig. 4] and in lowering tachycardia rates if SVA persisted [Fig. 5]. None of the agents as 2nd line therapy was associated with a greater rate of SVA termination although **sotalol** tended to be superior for AF. Once fetal SVA was converted to sinus rhythm, chronic drug therapy to birth with the drug(s) that successfully terminated the SVA was used to prevent recurrences. Recurrence of SVT and AF was documented in 8% and 15% of cases during the first month of maintenance treatment.

**Fig. 3. Freedom from termination of fetal AF (n=36):** For patients with AF, in multivariate models adjusted for arrhythmia pattern, 1st line sotalol was associated with a greater likelihood of AF termination compared with digoxin (HR: 5.4; p=0.05) or flecainide (HR: 7.4; p=0.03). Time to conversion of 50% was 12 days with sotalol, but not achieved with the other drugs before delivery.

**Fig. 4. Freedom from termination of fetal SVT (n=75):** For patients with SVT, in multivariate models adjusted for hydrops and SVT pattern, the use of flecainide (HR: 2.9; p=0.01) or digoxin (HR: 2.1; p=0.02) as 1st therapy were associated with increased likelihood of SVT termination compared to sotalol. The median time to conversion of 50% of cases was 3 days with digoxin, 4 days with flecainide but 12 days with sotalol.

**Fig. 5. Effects of 1st line treatment on tachycardia rates.** When incessant SVT (n=23) or AF (n=22) persisted to day 5 of treatment, ventricular rates were lowered more with flecainide and digoxin than with sotalol (p<0.001). This suggests that flecainide and digoxin are similarly effective in reducing the tachycardia to better tolerated rates while sotalol has no or only modest heart rate slowing effects.

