**3.2 SAMPLE SIZE CALCULATIONS.** Based on our survey results and the retrospective study by [name] et al, we expect 70% of SVA cases to be SVT (50% no hydrops; 20% hydrops) and 30% AF (25% no hydrops; 5% hydrops). Survey II suggests that an average of 2.3 SVT/no hydrops, 1.21 AF/no hydrops and 1.03 treated SVT/hydrops cases/year/center will be eligible for RCT enrolment, with average consent rates of 81%. Sample size calculation for 2-arm treatment comparisons was performed using PASS (Power and Sample Size) v12 (NCSS, LLC, Kaysville, Utah, USA). To calculate sample size requirements for this study we expected the proportion of patients with normal primary outcome to be 55% with SVT without hydrops, 30% with AF without hydrops, and 30% of SVT with hydrops with the inferior treatment arm (i.e. the null hypothesis). We aim to detect an improvement of +20% in the proportion of patients with a normal primary outcome with the superior RCT arm (i.e. 75% for SVT without hydrops; 50% for AF without hydrops and SVT with hydrops; i.e. the alternative hypothesis). The test statistic used is the two-sided Likelihood Ratio test which is equivalent to the Wald chi-square for logistic regression models which will be used to analyze our primary outcome. The significance level of the test of significance was targeted at 0.05, with a power of 80%. Assuming those metrics, we will need 550 RCT participants, with a minimum number of patients in each of the three RCTs of:

**AF without hydrops (RCT A):** 186 (93/arm) treated cases ← 232 approached cases with 80% consent rate

**SVT without hydrops (RCT B):** 178 (89/arm) treated cases ← 222 approached cases with 80% consent rate

**SVT with hydrops (RCT C):** 186 (93/arm) treated cases ← 232 approached cases with 80% consent rate

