**INCLUSION CRITERIA:**

- Mother has provided written informed consent to participate in the RCT
- Fetal AF *without* hydrops (RCT A) or SVT *without* hydrops (RCT B) or SVT *with* hydrops (RCT C)
- Tachyarrhythmia that is significant enough to justify immediate transplacental pharmacological treatment:
  - Tachycardia  $\geq 170$  bpm during  $\pm 100\%$  of time ( $\leq 30$  0/7 weeks of gestation)
  - Tachycardia  $\geq 180$  bpm during at least 10% of observation time
  - Tachycardia  $\geq 280$  bpm
  - Tachycardia with fetal hydrops
- Gestational age  $> 12$  0/7 weeks and  $< 36$  0/7 weeks at time of enrolment
- Untreated tachycardia at time of enrolment
- Singleton Pregnancy
- Healthy mother with  $\pm$  normal pre-treatment cardiovascular findings:
  - ECG within normal range (sinus rhythm; QTc  $\leq 0.47$ s; PR  $\leq 0.2$  s; QRS:  $\leq 0.12$  s; insignificant anomalies; isolated premature beats; isolated complete right bundle branch block; non-specific ST-T segment changes allowed)

- Maternal resting heart rate of 50 bpm or above
- Maternal systolic BP of 85 mm Hg or above

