#### EXCLUSION CRITERIA:

- AF *with* hydrops (condition is too infrequent to be studied in a separate RCT sub-study; eligible for Registry)
- Any maternal-fetal conditions associated with high odds of premature delivery or death other than tachycardia (e.g. severe IUGR; premature rupture of membrane; life-threatening maternal disease (incl. pre-eclampsia; HELLP syndrome); severe congenital fetal abnormalities (T 13 or 18; surgery or death expected < 1 month))
- History of significant maternal heart condition (open heart surgery; sick sinus syndrome; channelopathy (long QT, Brugada syndrome); ventricular tachycardia; WPW syndrome; high-degree heart block; cardiomyopathy)
- History of significant maternal obstructive airway disease including asthma
- Current therapy with the following medications:
  - antiarrhythmic drugs
  - Pentamidine
- Maternal serum potassium level <3.3 mmol/L / <3.3 mEq/L
- Maternal ionized serum calcium level of <1 mmol/L / <4 mg/dL) or total serum calcium level <2 mmol/L / <8mg/dL
- Maternal serum creatinine level > 97.2 µmol/L (>1.1 mg/dl)

**7.3 INFORMED CONSENT (IC)** The consent process at each site will be performed as approved by local REB or as per institutional practices. The study is explained to the patient in detail, including the alternatives (registry, non-participation) and any questions are answered prior to signing the consent form. The person obtaining consent must co-sign the form with date and time. A copy of the consent form must be given to the patient.

**7.4 PATIENT DATA ENTRY.** Completion of the enrolment and randomization process requires submission of the following baseline information into the patient's electronic REDCap form *prior* to any treatment:

- Name and center of the site investigator, incl. contact information
- SVA: date/gestational age at diagnosis, mechanism, pattern, rate and AV relationship
- Fetal state: presence/location of effusion(s), skin edema, and fetal movements
- Confirmation of enrolment into prospective randomized trial and selection of the sub-study
- Checklist of eligibility criteria for participation

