**SUB-ANALYSIS** will attempt to determine the factors associated with successful RCT outcomes. To accomplish this, we will use our primary outcome as the dependent variable. Fetal factors (age at diagnosis), SVA characteristics (heart rate; arrhythmia pattern; SVT subtypes) and treatment metrics (agent(s); dose) will be considered as potential independent variables. In a first, all variables will be evaluated separately in univariable

logistic regression models. Those with p-values <0.20 in those models will then be selected for further evaluation in a bootstrap bagging algorithm (500 random resamples). Those variables with high reliability (selected in >50% of the random resamples) will be included in a multivariable logistic regression model (PROC LOGISTIC) with likelihood ratio test to determine regression model fit, Wald chi-square test from maximum likelihood estimates (Fisher's scoring technique) to determine statistical significance of the therapy arm and c-statistic from the regression model's area under the curve (AUC) to measure model accuracy with backward selection of variable (p<0.05 to enter) to obtain a final model. Effect size estimate and standard error will be converted into odds ratio with 95% CI to facilitate comparisons of effect size between the different covariates. This final model would indicate factors associated with greater odds of positive outcome and, providing that analog results are found between the effects of 1st line therapy between the 2 models (primary RCT analysis as above and sub-analysis).

**FREQUENCY OF ANALYSIS.** Pre-specified interim analyses of the 3 strata will be performed separately at 50% of enrolment. Each analysis will focus on the primary outcome and safety report including review of between-groups differences and individual review of AEs, other maternal, fetal and infant outcomes, and other safety concerns, if any. All interim analyses will be blinded (with potential un-blinding at the request of the DSMB) as to not influence the final analysis.

**SUBGROUP ANALYSIS.** Additional subgroup analyses will include comparisons with registry participants and impact of tachycardia rates: 1) cardioversion rates over time of RCT participants with SVT and AF  $\pm$  hydrops; and 2) tachycardia rates of cases with persistent SVA at  $\pm$ 1 week of acute therapy (all arms).

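### The primary logistic model names no covariate; pre-specifying gestational age and SVA pattern, both recorded before treatment, is a low-cost efficiency gain (0 to about 7 points of power, depending on assumed prognostic strength)

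*Combined protocol and SAP*

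**What the plan says.** - **Primary analysis (section 7.11, Primary outcome).** The plan says "the proportion of participants in each therapy arm will be compared using logistic regression models (PROC LOGISTIC"). Significance of the arm is judged by a Wald chi-square, and the effect is given as an odds ratio with a 95% CI. No covariate is listed, and no confidence interval for the difference in proportions is planned.
- **Sizing (section 3.2).** The same two-arm comparison is sized without covariates. The target is on the absolute scale: "We aim to detect an improvement of +20% in the proportion of patients with a normal primary outcome".
- **Data held before treatment.** Section 7.4 requires, before any treatment, entry of "date/gestational age at diagnosis, mechanism, pattern, rate and AV relationship". Section 7.2 admits pregnancies beyond 12 and below 36 "0/7 weeks at time of enrolment".
- **Other uses of these variables.** The test of randomisation in section 7.11 covers "Baseline characteristics that should be equally distributed between groups through randomization (age at diagnosis, baseline fetal heart rate, incessant vs. intermittent SVA, maternal age"). The Sub-analysis lists age at diagnosis, heart rate, pattern, SVT subtype, agent and dose, which "will be considered as potential independent variables". It selects among them by a p<0.20 screen, bagging and backward selection.
- **Earlier evidence (section 2.5).** The previous non-randomised study compared drugs "in multivariate models adjusted for arrhythmia pattern" for AF and "in multivariate models adjusted for hydrops and SVT pattern" for SVT.

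**The concern.** Section 2.5 (summary) names mechanism and fetal state as main determinants of outcome. Running three separate RCTs already deals with both. Within each RCT, two plausibly prognostic baseline variables stay out of the primary model.

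- **SVA pattern.** The earlier study adjusted for it within AF and within SVT, although its outcome was cardioversion and not term delivery in normal rhythm.
- **Gestational age.** Entry spans about 24 weeks, against an endpoint fixed at 37 weeks. The documents do not give the direction or shape of the effect. It may not be monotone, because late entrants have little time to convert.

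The Sub-analysis does not fill the gap. Its covariates are chosen from the data, and it admits dose, which the physician may change after randomisation. It also looks for agreement with the primary analysis, but an arm-only odds ratio and a covariate-adjusted one differ even when nothing is wrong.

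What is at stake is precision in three trials each sized at the 80% threshold, and the influence of a chance imbalance on the primary estimate. The balance tests come with no rule for what follows an imbalance.

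**Working it through.** **1. The plan's own figure.** Inputs from section 3.2: two-sided alpha 0.05, power 80%, 30% v 50% (RCT A and C) and 55% v 75% (RCT B). The pooled two-proportion formula is

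n per arm = [1.960·√(2·p̄·(1−p̄)) + 0.842·√(p₁(1−p₁) + p₂(1−p₂))]² / (p₂−p₁)².

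- 30 v 50: [1.960·√0.48 + 0.842·√0.46]² / 0.04 = 93.0, so 93. Power at 93 is 80.0%.
- 55 v 75: [1.960·√0.455 + 0.842·√0.435]² / 0.04 = 88.1, so 89. Power at 89 is 80.4%.

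The stated sizes are reproduced (186 + 178 + 186 = 550). With the Wald test on the log odds ratio, power is 78.8% and 79.0%, so the choice of test moves the figure by about one point.

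**2. Power with both covariates.** The documents give no prognostic strength, so a range was assumed. Intercepts were solved so that marginal success stays at exactly 30 v 50% or 55 v 75%. The adjusted model is arm + age + age² + incessant. The table uses gestational age uniform on 18–36 weeks, 70% incessant, a linear age effect and 5,000 trials per scenario.

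| Strength | Log-odds: age per 5.2 weeks / incessant | 30 v 50%, 93/arm: arm-only → adjusted | 55 v 75%, 89/arm: arm-only → adjusted |
|---|---|---|---|
| None | 0 / 0 | 78.9 → 79.2% | 79.9 → 79.9% |
| Weak | 0.25 / −0.4 | 78.8 → 80.2% | 80.4 → 80.6% |
| Moderate | 0.5 / −0.8 | 79.7 → 82.8% | 80.3 → 82.5% |
| Strong | 0.8 / −1.2 | 79.3 → 86.3% | 80.1 → 86.5% |

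Other age distributions, 50–70% incessant and a hump-shaped age effect were also tried. The gain, grouped by the joint AUC of the two covariates, was:

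- none (0.50): −0.6 to +0.8 points
- weak (0.57–0.61): +0.2 to +1.8
- moderate (0.635–0.67): about +2 to +3
- strong (0.70–0.745): +3.3 to +7.0

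A hump-shaped effect gives similar gains provided the curved term is fitted. Scenarios above AUC 0.745 arose only when age was uniform over 12–36 weeks. They gave +6.9 to +15 points and are not relied on.

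**3. A second set of assumptions.** Gestational age normal, 60% incessant, 20,000 trials per scenario. Strength is given as odds ratio per SD of age / odds ratio for incessant.

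- 1 / 1: +0.4 (RCT A and C) and −0.4 (RCT B)
- 1.5 / 0.5: +2.6 and +1.9
- 2 / 0.33: +6.5 and +4.6
- 2.5 / 0.33: +7.6 and +6.2

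An extreme 3 / 0.25 gave +9.4 and +8.5. As a cross-check, put n/(1−R²) into the power formula for 30 v 50%. R² = 0.05 gives 93/0.95 = 97.9 per arm and 82.0%; R² = 0.15 gives 109.4 per arm and 86.0%. The simulated within-arm R² was 0.055–0.062 at 1.5 / 0.5 (simulated power 82.3%) and 0.132–0.145 at 2 / 0.33 (85.8%), which agrees.

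**4. Risk difference.** The relative efficiency of the standardised risk difference changes by about −2% (none), 0–1% (weak), 5–7% (moderate) and 15–17% (strong). At moderate strength that equals 0.05×186 to 0.07×186, about 9 to 13 participants. Its mean was 0.198–0.203 against a true 0.20, with CI coverage of 94.2–95.3%.

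**5. Type I error.** At 5,000 trials: 4.8–5.1% arm-only and 5.0–5.5% adjusted (simulation standard error √(0.05·0.95/5000) = 0.3 points). At 20,000 trials: 4.6–5.0% and 5.0–5.2%.

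**6. Odds ratio scale.** The design odds ratios are (0.50/0.50)/(0.30/0.70) = 2.33 and (0.75/0.25)/(0.55/0.45) = 2.45. For the same 20 points the conditional odds ratio is 2.49–2.64 at moderate and 2.69–2.90 at strong.

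**The case against.** The strongest reply is that nothing is broken. An unadjusted primary analysis of a randomised trial is legitimate, is correctly sized here, and already leaves no choice of covariates in the primary test. That stands, and it is why this point is an improvement only.

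The gain is assumed and leans on the less documented covariate. With pattern alone (70% incessant) it is only 0.7, 1.7 and 3.3 points at weak, moderate and strong for 30 v 50%, and 0.1, 0.9 and 1.3 for 55 v 75%. The rest comes from gestational age. Section 2.1 links younger age to hydrops, which the sub-studies already separate. This also stands, so the moderate figure is a fairer guide than the maximum.

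Adjustment has costs. The odds ratio becomes conditional, which weakens its planned use for comparing the trials. The documents give no threshold for incessant SVA. In RCT C pattern may hardly vary: at an assumed 95% incessant, about 2 to 3% of simulated fits failed through separation. These costs are real but small. A standardised risk difference, a written definition and a fallback rule deal with them.

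**Conclusion.** The point holds as a recommended improvement. The planned test is valid and has its stated power to within about a point, so no bias is being repaired. Pre-specified adjustment for gestational age and pattern would add roughly 0 to 7 points of power: about nil if neither is prognostic, and about 2 to 3 points at moderate strength. The top of the range needs strong covariates, for example an odds ratio of 2 or more per SD of gestational age together with about one third for incessant SVA. The documents neither establish nor exclude that. Confidence is medium, because every gain rests on assumed prognostic strength and an assumed covariate distribution. The downside is small: about 2% of efficiency in the risk difference if the covariates prove uninformative, with no material loss of power.

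**What to change.** In section 7.11, for each RCT:

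- Define the primary model as arm + gestational age at enrolment (continuous, with a quadratic or spline term) + incessant versus intermittent SVA, and test the arm term.
- Report the adjusted odds ratio, labelled conditional, beside the standardised risk difference with its 95% CI, to match the 20-point target in section 3.2.
- Keep the arm-only model as a sensitivity analysis, and name it as the fallback if the adjusted fit fails, which is most likely in RCT C.
- Define incessant, and state how a missing covariate is handled.
- Keep the Sub-analysis exploratory. Present baseline balance descriptively: under randomisation any difference arises by chance, and the tests lead to no stated action.

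Make the change before any unblinded comparison of arms, hence before the interim analysis at 50% of enrolment. The cost is SAP wording. Pattern and gestational age at diagnosis are already entered, and gestational age at enrolment is needed to confirm eligibility. The sample size stays at 186, 178 and 186.
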